2 LAY SUMMARY

Cardiovascular disease (CVD) is the leading cause of death in the US, however African American residents of rural areas in the south and southeast regions have the highest prevalence of CVD of any group. African Americans carry a significant burden of CVD risk factors that often co-occur; this burden is amplified in rural communities. CVD disparities at the intersection of race and geography are driven by individual risk behaviors and complicated by factors such as limited access to quality healthcare, socio-economic inequities, limited healthcare infrastructure and environmental barriers to behavior change. Interventions to ameliorate CVD burden in rural African American communities will require placing the individual in the context of the larger community and taking advantage of new technologies to support behavior change. However, how best to integrate mobile technology into existing evidenced based interventions (EBIs) is still an emerging field and social and physical environmental factors important in rural communities are rarely considered in existing EBIs. The proposed study will address this gap in the literature by determining the feasibility and efficacy of adapting an EBI to consider the environment in important in rural African American communities and determining the acceptability of mobile technology in these communities to support behavior change. The proposed study is built on the

strong foundation of Project GRACE's 8-year history of designing and testing interventions using a community-based participatory research (CBPR) approach, and individual and collaborative expertise in community-based CVD outreach, service and research. We have developed a phased CBPR study with a long-term goal to reduce rates of CVD in Eastern NC. The overall objective of this proposal is to assess feasibility of implementing an EBI, adapted to the needs and interests of a rural community in order to plan a large scale study. To that end our specific aims are to 1) expand and sustain a Project GRACE CVD coalition of community and academic stakeholders to develop successful CVD risk prevention strategies in rural communities; 2) conduct a mixed-method community needs and assets assessment based on: a) assemble, review and assess existing sources of CVD data; b) identification of community strengths and resources using a web-based survey of community, faith based, social service and healthcare organizations; c) determine the acceptability of components of CVD risk reduction EBIs and community members' perceptions of possible targets for intervention using focus group interviews; d) determine specific family influences (barriers and facilitators) on acceptability of EBI acceptability; 3) adapt PREMIER, a multi-component EBI using intervention mapping; and 4) conduct a small-scale randomized control trial to assess a) efficacy; and, b) feasibility and adaption of implementing adapted PREMIER in rural settings.

3 SYNOPSIS

Trial Title	Cardiovascular Outcomes of an Adapted Evidence-Based Intervention for Rural African Americans: Heart Matters Trial		
Internal ref. no. (or short title)	Heart Matters		
Trial registration	NCT02707432 Date of registration: March 14, 2016 https://clinicaltrials.gov/ct2/show/NCT02707432?term=[name]&draw=2&rank=2		
Funder	National Heart, Lung, and Blood Institute (NHLBI; 5R01HL120690)		
Trial Design	Randomized, controlled trial		
Trial Participants	African American adults (21 years or older) with at least one risk factor for cardiovascular disease.		
Sample Size	140		
Planned Trial Period	Total length of the project is 18 months. Participant's involvement will be a 12-month intervention with a 6-month follow-up.		
Planned Recruitment period	March 27, 2017 – February 28, 2019		
	Objectives	Outcome Measures	Timepoint(s)
Primary	To determine the effect of an adapted intervention, Heart Matters, on cardiovascular clinical outcomes.	Body weight	6 months
Secondary	To determine the effect of Heart Matters on secondary cardiovascular clinical	Systolic and diastolic blood pressures	6 months

	outcome		
Intervention(s)	Lifestyle modification consisting of interactive group and individual visit sessions targeting physical activity, weight loss, and nutrition.		
Comparator	No comparator intervention due to delayed control design.		

4 ABBREVIATIONS

AE	Adverse event
PI	Principal Investigator
CT	Clinical Trials
GCP	Good Clinical Practice

5 BACKGROUND AND RATIONALE

Purpose: To determine the effect of an adapted intervention, Heart Matters, on cardiovascular clinical outcomes.

Background: African Americans in the rural southeast are disproportionately affected by cardiovascular disease and associated risk factors. Despite evidence-based cardiovascular interventions targeting clinical or behavioral risk factors, geographic and racial disparities persist and continue to widen. Cardiovascular disease (CVD) is the leading cause of death in the United States (US) with an estimated 50% of individuals in the US expected to have CVD by 2030. African American residents in rural areas of the south and southeast (also called the “stroke belt”) have the highest prevalence of CVD compared to other populations. Furthermore, CVD prevalence rates for residents of rural areas (13.1%) are higher compared to those in urban areas (11.2%) of the US. In the setting of geographic disparities, striking racial disparities in CVD risk factors, morbidity and mortality are exacerbated. African Americans are disproportionately affected by a higher burden of CVD risk factors: high blood pressure, diabetes, smoking, high cholesterol, and physical inactivity. This heightened risk is prevalent in both youth and older age groups and has increased over time. While CVD disparities at the intersection of race and geography are driven by a disproportionate burden of individual risk factors, racial disparities in rural settings are amplified by associated factors, such as limited access to quality healthcare services, socio-economic burden, dwindling resources, insufficient health infrastructure, and physical barriers to access to care. There are numerous evidence based interventions (EBIs) that have focused on reduction in CVD risk factors. These interventions have often focused on primary prevention of individual risk factors such as hypertension, diabetes, lipids, physical activity, and diet quality. Many of these have been developed in urban centers, and only a few have included participants that are reflective of geographic and racial disparities in CVD risk.

Given the burden of co-morbidities in rural African American populations, interventions targeting only one behavior or risk factor are likely to be less successful than those using intervention components and concepts impacting multiple behaviors. There is a need for culturally adapted interventions that address multiple behavioral risk factors for CVD. Using a Community-Based Participatory Research (CBPR) approach, our team adapted and will implement an EBI to improve cardiovascular risk in African Americans living in a rural underserved setting.

Participants: African Americans who reside in Edgecombe and Nash counties, aged 21 years or older, with at least one self-reported cardiovascular disease (CVD) risk factor.

Potential benefits for study participants include participation in long-term lifestyle modifications that may result in improved diet, nutrition, and physical activity patterns, which in turn should decrease blood pressure and lead to an overall reduction in cardiovascular and cancer morbidity.

Heart Matters Intervention: Heart Matters will use a lifestyle modification to reduce CVD risk factors and includes 26 interactive group sessions and 7 individual visit sessions over 12 months. Heart Matters lifestyle goals include: 1) reducing weight by 15 lbs. or another agreed upon goal, 2) limiting fat intake by consuming 20–50% or less of total calories from fat, 3) limiting daily sodium intake to 2300 mg or less, 4) accumulating 150 min of moderate-intensity exercise each week, 5) limiting alcohol intake; women are advised to consume no more than one alcoholic drink per day and men are advised to consume no more than two alcoholic drinks per day, and 6) diet and physical activity tracking.

Trained facilitators and co-facilitators will conduct 26 90-minute group sessions at each organizational site with 15–20 participants per group. Facilitators are members of the community who are teachers, coaches, or clergy members and have 30 min of group supervision of adherence to protocol for each session delivered. Co-facilitators are allied health professionals, such as nutritionists, nurses, and personal trainers who help deliver the educational content. All facilitators will participate in an extensive three-part training on intervention protocols and curriculum.

Participants will have seven 60-min individual sessions throughout the intervention. Individual sessions will be pre-scheduled and conducted via phone by the facilitator. Using motivational interviewing techniques, facilitators will discuss participant’s progress and challenges to making behavior changes. Participants develop an individualized action plan at the first individual visit and this plan is revisited in subsequent individual visit sessions in an effort to track individual progress.

6 OBJECTIVES AND OUTCOME MEASURES

Objectives	Outcome Measures	Timepoint(s) of evaluation of this outcome measure (if applicable)

Primary Objective To determine the effect of an adapted intervention, Heart Matters, on body weight.
	
Body weight measured by Tanita WB-800 Professional Digital Weight Scale
	
Body weight measurement at day 0 and 6 months after baseline.

Secondary Objectives To determine the effect of an adapted intervention, Heart Matters, on cardiovascular clinical outcomes.
	
Systolic and diastolic blood pressures are measured by the Omron HEM907XL-Automatic Digital Blood Pressure Monitor.
	
All secondary outcomes are measured at day 0 and 6 months after baseline.

7 TRIAL DESIGN

Heart Matters is a community-based randomized trial comparing the effects of implementing the adapted lifestyle modification intervention on cardiovascular clinical outcomes among African American participants in rural eastern NC.

To implement Heart Matters, we will cluster individual participants within organizations that we recruit to participate in the study and be host sites for the intervention delivery. We will randomize organizations to 2 start times: Time 1 Heart Matters Intervention Group (immediately after baseline data collection) and Time 2 6 month-delay Heart Matters Intervention Group (6 months after baseline data collection). Randomization by organization will reduce the likelihood of data contamination given the fact that rural communities tend to be smaller and participants may be familiar with each other.

The flow of the participant is: 1. Screening at community organization and pre-intervention data collection. 2. Randomization of organizations to treatment group or 6 month delayed intervention control, 3. 6 month assessment data collection.

Data collection procedures: After the consent process, eligible individuals will complete the baseline data collection in a community setting. All data collection will be completed by trained research staff from the partner community organizations, James McFarlin Community Development, Inc and Project Momentum, Inc. Data collection will include biometric and biomarker data as well as self-report behavioral data. Trained research staff will collect biometrics such as weight, height, grip strength, and balance. Trained research staff who are registered nurses will collect blood pressure and hemoglobin A1c. Study staff will record the biometric data on paper forms which will be entered into REDCap, a secure web-based application for data management. For participants with life-threatening A1c levels, they will be immediately transported to emergency services, and adverse event data will be documented by research staff. The baseline questionnaire will include behavioral measures and structured questions on demographics (e.g. age, race, marital status, SES), health history, medications, CVD risk factors. Data collectors will enter data from the paper questionnaire forms into REDCap.

8 PARTICIPANT IDENTIFICATION

8.1 Trial Participants

Participants with at least one risk factor for cardiovascular disease, living in one of two rural counties in eastern North Carolina, aged 21 years and older.

8.2 Inclusion Criteria

- Participant is willing and able to give informed consent for participation in the trial.
- African American adults aged 21 years or above.
- Self-reported with at least one cardiovascular disease risk factor of pre-diabetes or diabetes, hypertension, obesity, family history of early CVD, or prior diagnosis of CVD

8.3 Exclusion Criteria

The participant may not enter the trial if ANY of the following apply:

- Individuals who had significant cognitive impairment or unstable cardiovascular disease

- Cognitive impairment that limits informed consent

9 TRIAL PROCEDURES

9.1 Recruitment

9.1.1 Organizational Recruitment

We will recruit organizations to serve as recruitment and intervention sites from both counties (Edgecombe and Nash). We will invite potential organizations based on: (a) existing relationships through the Project GRACE consortium, (b) and a list of organizations beyond existing networks generated by our James McFarlin Community Development, Inc and Project Momentum, Inc collaborators. Knowing that CVD risk is high in older adult populations, the extended list will include senior health and civic organizations. Historically, faith based organizations reach a large segment of the minority community and are a trusted leader in the community. As a result, many organizations may be faith-based.

In addition to partnering for participant recruitment, organizations will be host sites for intervention delivery. We will use the following inclusion criteria to evaluate each organization: kitchen space with refrigerator, stove and/or microwave, contact person from each organization available to open and close the building, and layout of how the used space should look at the conclusion of use. We will base final inclusion criteria on if the site could host the intervention for all 12 months. Of the original list of criteria, we will identify sufficient sites to meet sample size needed.

9.1.2 Individual Participant Recruitment

Community-based recruiters at James McFarlin Community Development, Inc and Project Momentum, Inc will work with organizational leaders to hold recruitment events at each organization. Outreach to individuals will be based on recommendations from organizational leaders and will include direct outreach and information sessions at each organization, distributing written materials/flyers, recruiting at organizational events and exploring the social networks of initial recruits.

9.2 Screening and Eligibility Assessment

We will obtain verbal informed consent from potentially eligible participants for the initial screening during which individuals will provide identifiable information (e.g. contact information) and provide medical history to determine if eligible or excluded. No re-screening or protocol waivers will be permitted. Medical history interview will ask about cardiovascular disease risk factors (pre-diabetes or diabetes, hypertension, obesity, family history of early CVD, or prior diagnosis of CVD) and cognitive impairment.

9.3 Informed Consent

After the eligibility screening, we will obtain written informed consent for each eligible participant who decides to enroll in the study. Community partners at James McFarlin Community Development, Inc and Project Momentum, Inc will be responsible for enrolling participants into the study.

9.4 Randomization

Participants in organizations will be randomized by a statistician into Time 1 (immediate intervention delivery after baseline data collection) and Time 2 (6 month delayed intervention delivery) under a matched pair in order to balance the sample size between Arm 1 and 2. Organizations will be paired based on the number of participants, and then randomly assigned one organization from each pair to each arm.

9.5 Blinding and code-breaking

There is no blinding or code-breaking in this trial.

9.6 Baseline Assessments

Immediately following the consent process, eligible individuals will complete the baseline data collection in a community setting. All data collection is completed by trained research staff from the partner community organizations, James McFarlin Community Development, Inc and Project Momentum, Inc. Data collection will include biometric and biomarker data as well as self-report behavioral data. Trained research staff will collect weight. Trained research staff who are registered nurses will collect blood pressure and hemoglobin A1c. Study staff will record the biometric data on paper forms which will be entered into REDCap, a secure web-based application for data management. For participants with life-threatening A1c levels, they will be immediately transported to emergency services, and adverse event data will be documented by James McFarlin Community Development, Inc and Project Momentum, Inc research staff.

Trained data collectors will conduct the structured survey. The baseline questionnaire will include behavioral measures and structured questions on demographics (e.g. age, race, marital status, SES), health history, medications, CVD risk factors. Data collectors will enter data from the paper questionnaire forms into REDCap.

9.7 Subsequent Visits

Data collection occurs at baseline and at each 6 month interval for 18 months.

9.8 Sample Handling

All samples for A1C will be disposed as biohazard material immediately after collection, reading, and recording is complete.

9.9 Early Discontinuation/Withdrawal of Participants

During the course of the trial a participant may choose to withdraw early from the trial at any time. This may happen for a number of reasons, including but not limited to:

- The occurrence of what the participant perceives as an intolerable adverse event.
- Inability to comply with trial procedures
- Participant decision due to circumstances outside of trial.

Participants may have the following two options for withdrawal;

- 1) Participants can withdraw from the study but permit data and samples obtained up until the point of withdrawal to be retained for use in the study analysis. No further data or samples would be collected after withdrawal.
- 2) Participants can withdraw completely from the study and withdraw the data and samples collected up until the point of withdrawal. The data and samples already collected would not be used in the final study analysis. (Any limits to this type of withdrawal where, for example analysis of their data or samples has already been integrated into interim results or dose escalation decisions etc. should be explained in the participant information sheet).

In addition, the Investigator may discontinue a participant from the trial treatment at any time if the Investigator considers it necessary for any reason including, but not limited to:

- Ineligibility (either arising during the trial or retrospectively having been overlooked at screening)
- An adverse event which requires discontinuation of the trial or results in inability to continue to comply with trial procedures

9.10 Definition of End of Trial

The end of trial is the point at which all the data has been collected and entered and no participant contact is needed.

10 SAFETY REPORTING

Safety reporting will be addressed during routing study team meetings and additional as needed meetings or communication. The PI and study coordinator will report any safety issues to the IRB. The IRB will be notified of any safety issues that necessitate reporting and possible protocol changes. Progress reports will be provided to the IRB at least annually, or as requested. All unanticipated problems or serious adverse events involving risk to human subjects will be reported. All collaborators, students, and employees assisting in this research study will be informed about these obligations.

10.1 Adverse Event Definitions

Adverse Event (AE)	Any untoward medical occurrence in a participant to whom a medicinal product has been administered, including occurrences which are not necessarily caused by or related to that product.
Serious Adverse Event (SAE)	
A serious adverse event is any untoward medical occurrence that:
 
 • results in death • is life-threatening • requires inpatient hospitalisation or prolongation of existing hospitalisation • results in persistent or significant disability/incapacity • consists of a congenital anomaly or birth defect*.

	Other 'important medical events' may also be considered a serious adverse event when, based upon appropriate medical judgement, the event may jeopardise the participant and may require medical or surgical intervention to prevent one of the outcomes listed above.
--	--

10.2 Adverse Events

In the event of an adverse event, the PI and study team will work with the IRB to determine a protocol for handling AE that may occur during the course of data collection and the intervention. Facilitators and data collectors will be trained to follow protocol procedures and report any AE to the primary investigator immediately.

11 STATISTICS

11.1 Statistical Analysis Plan (SAP)

The plan for the statistical analysis of the trial are outlined below. There is not a separate SAP document in use for the trial.

11.2 Description of Statistical Methods

Demographics and clinical measures will be described using means, standard deviations, frequencies, and percentages. T-tests will be used to compare group level characteristics of continuous variables. Pearson Chi-square tests will be used to compare categorical group comparisons. Treatment effects from baseline to 6 months post intervention will be analyzed using linear mixed effects models. Least square means differences will be used by finding the differences between baseline and 6-month outcomes, as well as differences in groups with corresponding 95% confidence intervals. Models will be adjusted for age, blood pressure medications, and cluster. All of the analysis will be implemented using SAS 9.4 (Cary, NC).

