11.3 Sample Size Determination

Sample size for Heart Matters was calculated on the basis of observing a 1.8 kg difference (SD = 3.2) in the primary outcome – weight change – between two intervention groups from baseline to 6 months. We determined a sample of 102 would allow us to detect a 1.8 kg difference (SD = 3.2) in weight change between intervention and control groups, with 80% power and an α of 0.05. Accounting for attrition and intra-class correlation, due to a clustered randomized delayed intervention design, we plan to enroll 120 participants.

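### Does section 11.2 place the primary analysis six months after the programme ends, rather than six months after baseline?

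*Combined protocol and SAP*

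**What the plan says.** Section 11.2 introduces the main analysis with "Treatment effects from baseline to 6 months post intervention will be analyzed using linear mixed effects models". The following sentence describes the estimates as obtained by "finding the differences between baseline and 6-month outcomes, as well as differences in groups".

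The time points elsewhere in the document are:

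- Section 6, primary outcome: "Body weight measurement at day 0 and 6 months after baseline". The secondary outcomes have the same timing, and the synopsis lists 6 months for both.
- Section 11.3: the sample size rests on a difference in weight change "between two intervention groups from baseline to 6 months".
- Section 5: the programme "includes 26 interactive group sessions and 7 individual visit sessions over 12 months".
- Section 7: one group starts directly after baseline. The other is described as "Time 2 6 month-delay Heart Matters Intervention Group (6 months after baseline data collection". The participant flow in the same section runs from baseline, through randomization of organizations to treatment or delayed-intervention control, to the 6-month assessment.
- Section 9.7: "Data collection occurs at baseline and at each 6 month interval for 18 months".

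**The concern.** The usual meaning of post intervention is after the intervention has finished. With a 12-month programme, 11.2 would then point to a different visit from the one section 6 defines for the primary outcome, and the two arms would reach that point at different calendar times.

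Two things would be at stake. First, at month 18 the delayed group has had the programme as well, so an analysis there would no longer compare treated with untreated participants. Second, a report that repeated the phrase could present a difference measured halfway through the programme as one that persisted six months after it ended.

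A related silence is that the delayed group's start and its 6-month assessment share the same nominal time. If the assessment came after the first sessions, the control group would no longer be untreated when weighed.

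**Working it through.** **Inputs.** Programme length 12 months (synopsis, section 5). Start at month 0 for the immediate arm and month 6 for the delayed arm (section 7). Visits at months 0, 6, 12 and 18 (section 9.7). Difference 1.8 kg, SD 3.2, 80% power, α 0.05 (section 11.3). A two-sided test and 1:1 allocation are assumed; section 9.4 pairs organizations by size and assigns one of each pair to each arm.

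**The plan's own figure.** The normal approximation gives n per arm = 2 × (1.960 + 0.842)² × (3.2/1.8)² = 2 × 7.85 × 3.16 = 49.6, rounded up to 50, or 100 in total. The two-sample t-test version gives 50.6, rounded up to 51, or 102 in total. This is the figure in 11.3, and power at 51 per arm is 80.3%. It was computed for weight change from baseline to 6 months.

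**Three readings of the phrase.**

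| Reading | Immediate arm | Delayed arm | Usable for a two-arm comparison? |
|---|---|---|---|
| 6 months after the programme ends | 0 + 12 + 6 = month 18 | 6 + 12 + 6 = month 24 | No. Month 24 is never observed, and by month 18 the delayed arm has completed its own 12 months |
| 6 months after the programme starts | 0 + 6 = month 6 | 6 + 6 = month 12 | No. The visits differ and both arms are treated |
| 6 months after baseline | month 6 | month 6 | Yes. Common visit, delayed arm not yet started |

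Only the third reading can be carried out as a randomized comparison. It is also the one given by section 6 and the one that fits the synopsis, the section 7 flow, 11.3 and the next sentence of 11.2. At that visit the immediate arm is 6/12 = 50% of the way through the programme.

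**Visit order.** One can construct a loss. Suppose the 1.8 kg accrues linearly over 26 weeks and only the delayed arm is weighed w weeks after its first session. The contrast is then 1.8 × (1 − w/26), which is 1.66 kg at w = 2 and 1.52 kg at w = 4. At 51 per arm without clustering, power would be 74% and 66%.

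The premise is not in the documents. If both arms were weighed w weeks late, the same linear assumption gives 1.8 × (26 + w)/26 − 1.8 × w/26 = 1.80 kg, with no dilution, because the immediate arm is still in its programme. The loss needs late weighing in the delayed arm alone, or an earlier start there, and neither is described. Nor are 74% and 66% this trial's power: they use 51 per arm and no design effect, while 11.3 plans to enrol 120 in a cluster design. These figures should carry no weight.

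**The case for a change.** The best case for a change has three parts. Section 11.1 states that there is no separate SAP, so no other analysis document puts the phrase right. The literal reading is not empty: month 18 is a scheduled visit, and the synopsis describes a 6-month follow-up after the 12-month intervention, so for the immediate arm the phrase coincides with a planned assessment. And replacing a few words costs almost nothing.

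What stands is that the phrase is imprecise. Even the generous reading, six months after the intervention begins, fits the immediate arm only.

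The rest does not amount to a fault in the analysis. The lack of a separate SAP matters less when the very next sentence of 11.2, "Least square means differences will be used by finding the differences between baseline and 6-month outcomes", identifies the outcome and section 6 defines it. No section names month 18 as an efficacy time point. The feared misreport would need an author to lift one phrase and disregard the defined primary outcome.

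On visit order, an explicit sentence would be a courtesy to site staff. However, the section 7 flow calls the second group a delayed-intervention control and puts the 6-month assessment next, which is naturally read as assessment before the first session.

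**Conclusion.** The phrase in 11.2 is a clerical slip for six months after baseline. An analyst working from the whole document would use the month-6 visit, because it is the time point defined for the outcome and the only one at which both arms share a visit with an untreated control. The effect on the contrast, sample size, power and results is nil, and 102 reproduces for the intended interval.

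The silence on visit order is a gap that the section 7 flow already fills, and no dilution can be attributed to it from the documents. These conclusions assume that the delayed organizations start no earlier than month 6 and are assessed before their first session, as section 7 implies. The reproduction of 102 further assumes a two-sided test with equal arms. No change to the plan is needed.

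### Section 11.2 reads most naturally as a change-from-baseline contrast: valid, and immaterial for weight, but a common-baseline-mean model would probably estimate the secondary blood pressure effects somewhat more precisely at little cost

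*Combined protocol and SAP*

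**What the plan says.** Section 11.2 is the only analysis text, because section 11.1 states: "There is not a separate SAP document in use for the trial". It specifies linear mixed effects models for the effect from baseline to 6 months, and then: "Least square means differences will be used by finding the differences between baseline and 6-month outcomes, as well as differences in groups". On covariates it says: "Models will be adjusted for age, blood pressure medications, and cluster". The baseline value of the outcome is not in that list. The section does not say whether the arms share a baseline mean, or whether cluster is a fixed or a random term.

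Section 11.3 sizes the trial on a 1.8 kg difference (SD 3.2) "in weight change between intervention and control groups", which fits a change contrast for the primary outcome. Section 6 lists systolic and diastolic pressure, at day 0 and 6 months, as the only secondary outcomes. Section 11.3 makes no power claim for them.

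On design, the participant flow in section 7 runs: "Screening at community organization and pre-intervention data collection. 2. Randomization of organizations to treatment group". Section 9.4 pairs organizations by number of participants and "randomly assigned one organization from each pair to each arm".

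**The concern.** A difference in change gives the baseline value a fixed coefficient of one. When the baseline and 6-month values are far from perfectly correlated, that over-corrects: part of any chance baseline difference between arms passes into the estimate. Over repeated randomizations this appears as extra variance. It is one loss, not a bias plus a loss of precision.

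For weight the correlation is so close to one that nothing is at stake. Blood pressure varies more within a person, so the loss there could be visible. With probably six or eight organizations those estimates will be imprecise anyway, and the baseline readings that would sharpen them are already being collected.

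**Working it through.** **The plan's own figure.** For 1.8 kg, SD 3.2, two-sided α 0.05 and 80% power, the normal approximation gives 2 × (1.960 + 0.842)² × (3.2/1.8)² = 49.6, so 50 per arm. The t-test calculation gives 79.5% power at 50 per arm and 80.3% at 51, so 102 in total. Section 11.3's 102 is reproduced.

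**Number of organizations (not stated).** Section 5 plans "group sessions at each organizational site with 15–20 participants per group", and section 11.3 says "we plan to enroll 120 participants". Assuming one group per organization, 120/20 = 6 and 120/15 = 8. If all organizations are paired, the number is even: 6 or 8. The synopsis gives 140 participants; then 140/20 = 7 and 140/15 = 9.3, so 8.

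**Formula, variances known.** In units of the variance of the baseline difference between arms, the change contrast has variance 2(1 − R) and the best use of baseline has 1 − R². Their ratio is (1 + R)/2, below 1 for any R below 1. The excess, 2(1 − R) − (1 − R²) = (1 − R)², is the carried-over imbalance.

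**Weight.** R is approximated by r = 1 − 3.2²/(2 × SD²), and the saving is (1 − r)/2. The baseline SD is assumed.

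| Assumed SD (kg) | r | Variance saved |
|---|---|---|
| 15 | 0.977 | 1.1% |
| 20 | 0.987 | 0.6% |
| 25 | 0.992 | 0.4% |

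At 51 per arm, ignoring clustering, power moves from 80.3% to 80.5–80.8%.

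**Blood pressure.** All of these inputs are assumed: correlation r between baseline and 6 months 0.5–0.7; ICC 0.01–0.05; persistence p of organization effects 0.5–1.0. With m participants per organization:

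- rs = (r − ICC × p)/(1 − ICC)
- R = [m × ICC × p + (1 − ICC) × rs]/[1 + (m − 1) × ICC]

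Example with 6 organizations of 20, r = 0.5, ICC = 0.05, p = 1: rs = 0.45/0.95 = 0.474; R = (1 + 0.45)/1.95 = 0.744; ratio = 0.872. Over the whole grid the ratio is 0.750–0.923 for 6 × 20 and 0.750–0.912 for 8 × 15. At r = 0.8 it is 0.83–0.95.

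**Variances estimated.** With few organizations the variance components are poorly estimated and some of that gain is lost. Simulations used REML with non-negative components and balanced, complete data, over the same grid at N = 120:

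| Method, variance relative to the change contrast | 6 × 20 | 8 × 15 |
|---|---|---|
| Common baseline mean | 0.79–1.00 | 0.78–0.97 |
| Participant's own baseline as covariate | 0.76–1.03 | 0.76–0.97 |
| Organization-mean baseline as covariate | 1.14–1.39 | 0.94–1.14 |

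- The first row gives the saving of about 0–22%. Its ranges span two separate simulation runs; the larger, with 40,000 trials per setting, gave 0.79–0.97 and 0.78–0.95. At N = 140 (8 × 17.5) the range was 0.77–0.95.
- At r = 0.8, a smaller simulation (1,500 trials per setting) gave a saving of about 2–14%.
- The weak case is 6 organizations, ICC 0.05 and full persistence. The saving is 0–6%; at r = 0.5 the systolic sampling SD goes from 3.29 to 3.18 mmHg.
- Over the r = 0.5–0.7 grid, for systolic pressure (assumed SD 18 mmHg, N = 120), the sampling SD of the effect goes from 2.5–4.6 to 2.4–4.1 mmHg with 6 organizations, and from 2.5–4.3 to 2.4–3.8 mmHg with 8.
- Coverage of 95% intervals, using t on (organizations − 2) degrees of freedom, was 0.96–1.00 for both analyses. The gain is not bought by undercoverage.
- If components may go negative, the gain at 6 organizations largely disappears: the ratio is 0.95–1.08, or 1.17–1.67 with a pair term.

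**Fixed cluster terms.** If organization is a fixed effect, each organization's level is free and the common-baseline constraint adds no information. A numerical check confirmed that the estimate is then identical to the difference in change.

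**The case against.** The strongest reply is that nothing here is an error. Both estimators are valid, the primary outcome is untouched, and the plan promises no power for blood pressure, so this is a preference between methods. It is right that there is no error. The point still has value, because it names a likely more precise method that uses data already collected.

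Second, the reading is least secure where it matters. Section 11.3 supports a change contrast for weight; for blood pressure, section 11.2 stands alone and could accommodate a common baseline mean. This stands as a caveat. The change contrast is the natural reading, but the saving applies only under it.

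Third, the size rests on assumptions, and on simulations with balanced, complete data. Section 11.3 expects attrition, and section 9.4's pairing by size suggests that organizations will differ in size. No result is available under those conditions. This stands too.

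Fourth, retaining cluster as a fixed adjustment would cancel the remedy, and an organization-by-time effect, which section 11.2 does not name, may widen intervals compared with a model lacking it. Both are correct. The quoted savings compare analyses within one variance structure.

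A reader might go further and infer that the change contrast is biased, or that the primary analysis loses power. The documents support neither. Section 7 places baseline collection before randomization, so the arms have equal expected baseline means, and for weight the two analyses nearly coincide.

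**Conclusion.** The point holds as a minor precision improvement for systolic and diastolic pressure only. The direction follows from the algebra when variances are known; the size does not come from the documents. The main range of about 0–22% of variance depends on the assumed correlation, ICC, persistence and number of organizations, and on balanced, complete data. A reader who expects a correlation near 0.8, or six organizations with stable differences between them, should expect little. Section 11.3's 102 is unaffected: under a common baseline mean, the 6-month difference between arms and the difference in change are the same quantity.

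**What to change.** In section 11.2, state for systolic and diastolic pressure, and for weight for consistency:

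- A linear mixed model of the baseline and 6-month values, with the arms constrained to a common baseline mean. Give the justification: all baselines are collected before organizations are randomized. The constraint depends on that order being kept.
- A participant effect, and random organization and organization-by-time effects, with variance components held non-negative. These replace any fixed cluster term.
- Adjustment for age and blood pressure medications as already planned.
- The treatment effect is the 6-month between-arm difference with its 95% CI.

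A simpler acceptable alternative is the 6-month value adjusted for the participant's own baseline, with a random organization effect. It can be up to about 3% worse in variance.

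An organization-mean baseline covariate is not proposed. It costs one between-organization degree of freedom, which raises the t critical value from 2.776 to 3.182 with 6 organizations and from 2.447 to 2.571 with 8. With a pair term it rises from 4.303 to 12.706 and from 3.182 to 4.303.

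The cost is one or two sentences, with no new data, visits or participants. The common-baseline model spends no between-organization degree of freedom on baseline. The downsides are a possible zero gain and the wider intervals that the organization-by-time effect may bring.
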